7.4 Exploratory Endpoints

The following exploratory endpoints will be evaluated:

Objective cognitive impairment correlated with subjective reports of cognitive impairment as measured by administered questionnaires.

Amyloid plaque burden using regional semi-quantitative determinations is associated with greater objective cognitive impairment.

Those individuals with the most profound cognitive impairment may have associated regional FDG metabolic changes consistent with neuronal loss or damage.

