10.1.2 FDG Fully-Quantitative Assessment

Compartment modeling techniques will be applied to the dynamic PET data to obtain estimates of kinetic rate parameters (K_1 , k_2 - k_4) and FDG net uptake (K_{net}). Individual rate parameters will be computed using full compartment-modeling techniques according to the two-tissue compartment model shown below. The commercially available PET analysis software (e.g. PMOD Technologies LTD., Zurich, Switzerland) will be used. The net uptake parameter will be computed from both full compartment modeling and Patlak graphical analysis^{139,140} both of which are standard and accepted methods.

A region-of-interest (ROI) will be drawn over the defined cortical brain region on the summed static FDG PET image. The summed image will be co-registered and fused to the patient's MRI. This will allow for regional determination of brain glucose metabolic rates. For each ROI the metabolic rate obtained can then be correlated with available clinical data, neuropsychological data, and the regional amyloid plaque burden SUV.

10.2 [¹⁸F]Flutemetamol-PET Imaging

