The primary assessment of amyloid plaque burden will be with visual assessment of abnormal cortical flutemetamol uptake as outlined in the recently approved Vizamyl (flutemetamol F 18 injection) prescribing information (section 2.5).¹ This will be a binary assessment of the images being positive or negative for increased and abnormal flutemetamol uptake and thus increased amyloid plaque burden. A secondary analysis of flutemetamol binding will occur using a regional semi-quantitative technique as described by Vanderberghe et al.¹²³ In this technique, a semi-quantitative global composite of standardized uptake value ratios (SUVRs) in the cerebral cortex which is obtained and normalized to the cerebellum or pons. The following regions are averaged to yield the global composite: lateral frontal, lateral temporal, lateral parietal, anterior cingulate, and posterior cingulate. This will yield a global composite for [¹⁸F]Flutemetamol-PET data. GE proprietary software (CortexID Suite) is available in our laboratory and will be used to determine both regional SUV values and a composite SUVR for [¹⁸F]Flutemetamol uptake. This database also contains [¹⁸F]Flutemetamol scan data from 105 healthy volunteers and has been validated to be over 99% concordant with visual reads using 172 scans from AD, MCI, and healthy controls using a threshold Z score of 2 (which corresponds to a composite SUVR of 0.59). This software will provide the control population to which we will compare our symptomatic CICI patients. Z scores obtained for the study patients using this software will then be correlated with available clinical data, neuropsychological data, and the regional FDG Z scores or metabolic rates.

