The imaging parameters will include the Z score values from Cortex ID for FDG and Z scores, regional SUV values and the composite SUVR for [¹⁸F]lutemetamol from CortexID.¹⁴⁶ For FDG these particular values are in comparison to an age-matched cohort so by definition they define a degree of FDG uptake reduction from normal. For [¹⁸F]Flutemetamol there is no specific age-related deposition in the database to assess age-matched normality so the study images will be compared the database control group as a whole to determine the Z scores compared to clinically negative amyloid scans. Z score values both regional and global for FDG and composite ([¹⁸F]Flutemetamol) can then be correlated with the various neuropsychological variables and clinical variables obtained to assess for differences and trends. The data will be analyzed descriptively using summary statistics and paired t-tests. Means, standard deviations and confidence intervals will also be reported. Scatterplots and bivariate summaries such as Pearson correlation coefficient and scatterplots will be used to characterize pairs of imaging parameters.

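### Regional flutemetamol uptake is named as SUV while only the composite is a reference-region ratio (SUVR), so the exploratory regional amyloid correlations, run as written, would tend to be attenuated or biased

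*Combined protocol and SAP*

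**What the plan says.** Three places in the protocol name the regional flutemetamol measure, and each calls it SUV.

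- Section 10.1.2 says that the metabolic rate in each FDG region can be correlated with clinical data, "neuropsychological data, and the regional amyloid plaque burden SUV".
- Section 10.2 says that the CortexID software "will be used to determine both regional SUV values and a composite SUVR".
- Section 10.4 lists the imaging parameters for flutemetamol as Z scores, "regional SUV values and the composite SUVR". It then says that pairs of imaging parameters will be summarised by Pearson correlation and scatterplots.

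Section 10.2 describes the secondary amyloid analysis as a regional semi-quantitative technique. What it defines is a global composite of SUVRs, "obtained and normalized to the cerebellum or pons". No reference region is stated for the regional values.

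Other sentences bear on which amyloid variable is correlated with what.

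- Section 10.2 ends: "Z scores obtained for the study patients using this software will then be correlated with available clinical data". The same sentence adds neuropsychological data and regional FDG Z scores or metabolic rates.
- Section 10.4 names, for correlation with the neuropsychological and clinical variables, "Z score values both regional and global for FDG and composite" for flutemetamol.
- Exploratory endpoint II, in sections 7.4 and 10.4, reads: "Amyloid plaque burden using regional semi-quantitative determinations is associated with greater objective cognitive impairment". It names no metric.

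**The concern.** An SUV is scaled to injected dose and body size, but it is not divided by uptake in a reference tissue. Anything that raises or lowers uptake in target and reference tissue together therefore stays in it: tracer delivery, error in the measured dose, and whatever body-size dependence the SUV scaling leaves. A ratio to a reference region cancels these. The plan relies on that elsewhere: the flutemetamol composite is a ratio, and section 10.1.1 normalises FDG to the pons.

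Sections 10.2 and 10.4 each put SUV and SUVR side by side in one sentence. An analyst would reasonably take the two terms as different and export regional SUV. The regional amyloid-FDG correlation, and any Pearson pair involving regional amyloid, would then use a noisier measure than the SUVR technique that section 10.2 adopts. With 12 evaluable patients there is little room for that. A real regional association could be missed, or one could appear because the shared factor is itself related to the other variable.

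**Working it through.** **1. The plan's own figure.** The only power statement is for the primary test in section 10.5: n = 12, reject at 4 or more positive scans, null 12%, alternative 42%, one-sided 0.05, stated power 80%. Exact binomial:

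- P(X ≥ 4 | 12, 0.12) = 0.0464
- P(X ≥ 4 | 12, 0.42) = 0.815

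The stated figure is reproduced. Section 10.4 bases this test on the composite SUVR (0.59, Z = 2), so the choice of regional metric does not change it.

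**2. Which amyloid variable is specified for each regional analysis?**

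| Analysis | Where | Amyloid variable named |
|---|---|---|
| Regional FDG rate against amyloid | 10.1.2 | Regional SUV |
| Regional FDG Z or rate against amyloid | 10.2 | Z scores, not stated to be regional |
| Pairs of imaging parameters (Pearson) | 10.4 | From a list that includes regional SUV |
| Cognition against amyloid | 10.4 | Composite Z |
| Endpoint II: regional amyloid against cognition | 7.4, 10.4 | None named |

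Two sections thus give different amyloid variables for the amyloid-FDG correlation. Endpoint II calls for a regional measure, and SUV is the only amyloid measure that the plan expressly labels regional.

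**3. Illustration of attenuation.** Write ln(SUV) = ln(SUVR) + ln(F), where F is the subject-level factor that a reference region would cancel. Suppose F is independent of SUVR and of the other variable. Then, on the log scale,

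r_observed = r_true × √[s² / (s² + f²)], with s² = ln(1 + CV_SUVR²) and f² = ln(1 + CV_F²).

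Inputs:

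- CV_SUVR: the documents give none for [18F]flutemetamol. As a stand-in, section 4.2.2 gives frontal [11C]flutemetamol DVR of 1.10 ± 0.15 in normal subjects (CV 0.15/1.10 = 13.6%, s² = 0.0184) and 1.56 ± 0.41 in AD subjects (CV 0.41/1.56 = 26.3%, s² = 0.0668). This is a different radiolabel and a different ratio, so it serves only as illustration.
- CV_F: not in the documents. Assumed 10% to 30%, so f² runs from 0.00995 to 0.0862.
- r_true = 0.60: an arbitrary example.

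| Spread used | CV_F | Multiplier | r = 0.60 appears as |
|---|---|---|---|
| Normal subjects | 10% | √(0.0184/0.0284) = 0.81 | 0.48 |
| Normal subjects | 30% | √(0.0184/0.1046) = 0.42 | 0.25 |
| AD subjects | 10% | √(0.0668/0.0767) = 0.93 | 0.56 |
| AD subjects | 30% | √(0.0668/0.1530) = 0.66 | 0.40 |

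**4. What this means at n = 12.** Two-sided p < 0.05 needs |r| > t/√(10 + t²) with t = 2.228, which is 0.576. By Fisher z (mean 3 × atanh r, critical value 1.96), power at r = 0.60 is about 55%. At the attenuated values it is 35% and 12% (normal-subject spread), or 47% and 24% (AD spread). A true 0.60 just exceeds the critical value, but all four attenuated values fall below it.

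**The case against.** The strongest reply is that the plan already names Z scores. The closing sentence of section 10.2 correlates CortexID Z scores with clinical, neuropsychological and FDG data, and section 10.4 names the composite flutemetamol Z score for the cognitive variables. This stands in part. A reader might infer that the plan will correlate regional SUV with cognition, but no sentence says so; it follows only indirectly from endpoint II. The reply does not remove the explicit regional SUV in section 10.1.2, and a composite Z score cannot serve an endpoint that asks for regional values.

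Second, SUV may be shorthand for SUVR. Section 4.2.1 describes SUV-based uptake ratios, and regional ratios are a natural component of the composite in section 10.2. This is possible. However, section 4.2.1 states the cerebellar reference explicitly, whereas sections 10.1.2, 10.2 and 10.4 give none for regional values, and two of them contrast the terms. If shorthand was meant, the text still needs correcting.

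Third, a reader might take regional SUV to be un-normalised and dominated by body weight. That goes too far: a standardized uptake value is already scaled to dose and body size, so only residual dependence remains.

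Fourth, the illustration depends on an unsourced factor CV and on DVR spreads from another radiolabel, and it assumes that the factor is unrelated to the other variable. If that assumption fails, the bias can go either way. All of this stands. Finally, these analyses are exploratory, section 10.4 treats the data descriptively, and no power is claimed for them.

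**Conclusion.** The concern holds as a specification defect in the exploratory regional analyses. As written, regional amyloid is SUV, only the composite has a reference region, and section 10.1.2 puts regional SUV directly into the amyloid-FDG correlation. If that is carried out literally, attenuation is the expected direction when the shared factor is unrelated to the other variable, and bias of either sign is possible when it is related.

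The size cannot be derived from the documents. The multiplier of 0.42 to 0.93, and hence 0.25 to 0.56 for a true 0.60, rests wholly on the assumed 10-30% factor CV and the stand-in DVR spreads.

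It would be tempting to conclude that the correlations are in fact diluted, or that the amyloid-cognition result is compromised. The documents do not support either: loose terminology remains possible, and the cognition variable that section 10.4 names is the composite Z score. For endpoint II, the supported conclusion is that its regional metric is unspecified. The primary test keeps its exact type I error of 0.0464 and power of 81.5%. The change is still worth making, because correlating these imaging measures is the stated objective in section 1.2.

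**What to change.** 1. In sections 10.1.2, 10.2 and 10.4, replace regional SUV with regional SUVR.
2. Choose one reference region, since section 10.2 leaves cerebellum or pons open. Use it for both regional and composite values, and make it consistent with the 0.59 composite threshold in section 10.4.
3. Name regional SUVR (or regional Z, if the software provides it) as the amyloid measure for endpoint II and for the regional amyloid-FDG correlation, so that sections 7.4, 10.1.2, 10.2 and 10.4 agree.

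The cost is wording, plus re-export of regional values if any have already been taken as SUV. No new scan, software or patients are needed, and the sample size and primary analysis do not change.

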10.5 Justification of Sample Size

Twelve evaluable patients (defined as having complete imaging and blood data available) will be enrolled in this study. By definition, 100% of evaluable patients enrolled will receive the complete set of PET studies [¹⁸F]Flutemetamol, FDG, and MRI. Due to blood drawing issues the total enrollment will need to be approximately 15 subjects to assure that complete blood and imaging data sets in 12 participants will be available for analysis. The data from Vandenberghe al. found that in a group of fifteen cognitively intact healthy volunteers over 55 (mean age 68.7) only one healthy volunteer had a positive amyloid scan.¹²³ Based on this data using a population similar in age to the expected experimental cohort, our null hypothesis (H_0) is that 12% of study participants will have amyloid positivity. With 12 patients we will have 80% power to reject H_0 at the nominal 0.05 one-sided significance level provided the true proportion of subjects with amyloid positivity is 42%. The null hypothesis will be rejected if 4 or more out of 12 patients show amyloid positivity. We will not image a separate control population in this study. The CortexID software contains a database of [¹⁸F]Flutemetamol scan data from 105 healthy volunteers¹³⁴ and will serve the function of a control group for the purposes of this exploratory study. The CortexID database has been validated in a subsequent study using [¹⁸F]Flutemetamol scans from 345 AD, MCI, or cognitively normal individuals.¹³⁴

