1.3 Hypotheses to be Tested - Synopsis

It is our hypothesis that individuals who are experiencing CICI may have a greater than expected prevalence of amyloid plaque burden when compared to individuals who are not experiencing cognitive complaints. The chemotherapy may accelerate the process of amyloid plaque burden deposition and subsequent possible neuronal injury and loss in individuals who have undergone chemotherapy.

The initial goal of our interdisciplinary group of imagers, oncologists, neurologists, neuropsychologists, and biostatisticians is to obtain “proof of concept” pilot data for eventual submission of a National Cancer Institute Quick-Trial for Imaging and Image-Guided Interventions: Exploratory Grant (R10) depending on the results of this pilot study.

The overall objective is to use [¹⁸F]Flutemetamol, FDG-PET, and fMRI to better understand CICI, which effects up to 16 -50% of individuals receiving long-term adjuvant chemotherapy.^{2,3} To date there have been few studies examining this problem using multi-modality imaging techniques to better understand this complex and significant problem.

FDG-PET and fMRI are routinely used in clinical practice for the evaluation of cognitive dysfunction in older populations complaining of memory dysfunction. It is well recognized that

FDG-PET can assist with the differentiation and characterization of various cognitive disorders due to unique patterns of cerebral metabolism caused by various cognitive and dementia-causing disorders.⁴⁻⁶ FDG-PET has been studied extensively in dementia research and has a high reliability in detecting Alzheimer's disease (AD) many years before it can be diagnosed reliably using clinical criteria.⁴

To our knowledge, there has been only a single small study using FDG-PET and bolus water activation paradigms in cancer patients complaining of memory problems.⁷ To date, there have been no studies using [¹⁸F]Flutemetamol as a PET imaging agent to assess the possibility of increased amyloid plaque burden as a potential contributing factor to the cognitive deficits and complaints seen in patients experiencing CICI. The novel feature of this project is in the combined use of [¹⁸F]Flutemetamol-PET, FDG-PET, and fMRI to study a poorly understood but common problem: cognitive impairment in breast cancer patients treated with chemotherapy.

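### Does the 12% null in section 10.5 need changing because the control data cited for it give 1 in 15 (6.7%)?

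*Combined protocol and SAP*

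**What the plan says.** Section 10.4 names an exact one-sample binomial test as the primary analysis, with a scan counted as positive at a composite SUVR of 0.59 or more. It quotes two background figures: up to 33% in cognitively normal elderly people, and one positive among fifteen volunteers in a somewhat younger group.

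Section 10.5 repeats the second figure: "fifteen cognitively intact healthy volunteers over 55 (mean age 68.7) only one healthy volunteer had a positive amyloid scan". It continues: "Based on this data using a population similar in age to the expected experimental cohort, our null hypothesis (H_0) is that 12" (per cent). It claims 80% power at a nominal one-sided 0.05 level "provided the true proportion of subjects with amyloid positivity is 42" (per cent), and gives the rule: "The null hypothesis will be rejected if 4 or more out of 12 patients show amyloid positivity".

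The same section says "We will not image a separate control population in this study" and assigns the role of control group to the CortexID database of 105 healthy volunteers. Section 10.4 adds that for flutemetamol "there is no specific age-related deposition in the database to assess age-matched normality".

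Sections 8.2 and 8.3 admit women aged 18 to 70. Section 8.3 excludes older women because amyloid positivity becomes more common even without cognitive problems.

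**The concern.** One in fifteen is 6.7%. No count out of fifteen gives 12%, since the next possible value is 2/15 = 13.3%. The plan states no confidence bound, shrinkage or rounding rule that leads from one figure to the other. The age claim is also bare: the volunteers were over 55 with mean age 68.7, only 70 − 68.7 = 1.3 years below the trial's upper limit, and no age mix is forecast for the patients.

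This matters because the trial has no concurrent controls. The hypothesis in section 1.3 is that patients "may have a greater than expected prevalence of amyloid plaque burden when compared to individuals who are not experiencing cognitive complaints", and in a one-sample test that expected prevalence enters through the null rate. A wrong null would put the threshold in the wrong place. The sharpest case is 3 positives in 12. That is not a rejection of 12%, and a reader who took 12% to be the observed control rate might conclude that there is no excess over those controls, although their rate was 6.7%.

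**Working it through.** **Inputs.** From section 10.5: n = 12, null rate 12%, alternative 42%, reject at 4 or more, one-sided 0.05, control data 1/15. From section 10.4: exact binomial test, other background figure up to 33%.

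**Step 1: reproduce the plan's figures.** With X ~ Bin(12, p), P(X ≥ 4) = 1 − Σ C(12,k) p^k (1−p)^(12−k) for k = 0 to 3.

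- At p = 0.12 the terms for k = 0, 1, 2, 3 are 0.2157, 0.3529, 0.2647 and 0.1203. They sum to 0.9536, so the size is 0.0464.
- P(X ≥ 3) at 0.12 is 0.1667, so 4 is the correct critical value.
- At p = 0.42, P(X ≥ 4) = 0.8147, which agrees with the stated 80%.

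**Step 2: compare 12% with the cited data.** 1/15 = 0.0667, with exact (Clopper-Pearson) 95% interval 0.0017 to 0.3195. The value 0.12 lies well inside it, and also between 6.7% and 33%. A simple shrunken estimate, (1+1)/(15+2) = 11.8%, comes close, but the plan does not say this was used.

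**Step 3: how the rule behaves if the background is not 12%.**

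| Background rate | P(X ≥ 4) | P(X ≥ 3) |
|---|---|---|
| 6.7% | 0.006 | 0.041 |
| 10% | 0.026 | 0.111 |
| 12% | 0.046 | 0.167 |
| 13% | 0.060 | 0.198 |
| 15% | 0.092 | 0.264 |
| 20% | 0.205 | 0.442 |

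The planned rule holds 5% up to a background of 12.3%.

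**Step 4: what a literal 6.7% null would do.** The exact 5% rule would become 3 or more in 12, with size 0.041 and power 0.936 at 42%. That rule holds 5% only up to a background of 7.2%. Taking 1/15 at face value would gain about 12 points of power (0.936 − 0.815) and leave almost no protection if the background is slightly higher.

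**Step 5: the result 3/12.**

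- P(X = 3) is 0.1203 at 12% and 0.1211 at 42%, a likelihood ratio of 0.1211/0.1203 = 1.01.
- The exact 95% interval for 3/12 is 5.5% to 57%, which contains 6.7%, 12% and 42%.
- The one-sided p-value is 0.167 against 12% and 0.041 against a fixed 6.7%.
- Fisher's one-sided test of 3/12 against 1/15, which allows for the uncertainty in both, gives (C(12,3)·C(15,1) + C(12,4))/C(27,4) = (3300 + 495)/17550 = 0.22.

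The inconclusiveness of 3/12 comes from having 12 patients and alternatives of 12% and 42%. It would be the same if 12% had a perfect citation.

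**The case for a change.** The strongest case for a change is that the text says the data gave 12%, and they did not. A cautious null protects against a false rejection. It does not protect against misreading a non-rejection, and the trial is meant to supply pilot data for a grant application. The rule also has little room above 12%: its size is already 6.0% at 13%. On this view the plan should state its source, fix an interval for the prevalence in advance, add a p-value at 6.7%, and commit to calling 3/12 inconclusive.

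Some of this stands. The derivation is missing, and the age similarity is asserted without support. The upper limit of 32% for 1/15 means the cited data alone cannot exclude a background above 12%.

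The rest does not lead to a change. The plan prints the 1/15 count in the sentence before the null, so no reader is misled about the control rate, and nowhere does it say that a non-rejection will be reported as no excess. Intervals are already promised in general terms: "Means, standard deviations and confidence intervals will also be reported". On the reasoning of section 8.3, a cohort younger than the volunteers would have a lower background, which makes 12% more cautious. A lone p-value at 6.7% would treat an estimate from fifteen people as known and would look only in the direction that favours rejection: at 3/12 it gives 0.041 where the two-sample comparison gives 0.22. Naming a source for 12% would not widen the rule's margin either.

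**Conclusion.** No change follows. The plan leaves the origin of 12% unexplained, but its arithmetic is right: size 4.6% and power 81.5% reproduce the stated 0.05 and 80%. Compared with the cited 6.7%, the null is on the cautious side (size 0.6%), and the price is power of 81.5% instead of 93.6% at 42%. That is a fair trade when the control estimate rests on fifteen people. An author of the study report can give 1/15 beside the observed prevalence and its exact interval without any amendment.

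This rests on two assumptions. The first is that the background in these patients is not materially above 12%. The plan's age reasoning supports this, though the documents give no figure to confirm it; at 15% the size would be 9.2% and at 20% it would be 20.5%. The second is that the volunteer's positive scan was judged by a criterion comparable with the SUVR cut-off, which the documents do not state. Adding a source for 12% would settle neither.
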